**3. Clarification for the required number of oral ulcers (Protocol Summary, Section 7.2)**

The required number of oral ulcers at screening AND at baseline are clarified to eliminate misinterpretation. All subjects must have at least 2 oral ulcers at Visit 1. Once 3 oral ulcers are observed, regardless of the time interval from the screening visit (ie, the interval of 2 weeks is not required) a subject is qualified to be randomized provided all other eligibility criteria are met. If only 2 oral ulcers are present at Visit 2, then at least 14 days must have passed since Visit 1 before the subject may be randomized.

**4. Clarification on the Static Physician's Global Assessment of Skin Lesions (Appendix G)**

The wording on scoring of severity of skin lesions as described in Appendix G, Static Physician's Global Assessment of Skin Lesions is revised. The protocol describes the scoring of the severity of skin lesions by the number of nodules/lesions present at one anatomical site. Since lesions can occur at different anatomical sites during the course of the study, it is more feasible to assess and score the lesions all together. As such, scoring of the number of nodules/lesions will be based NOT on one anatomical site at a time but at any anatomical site with respect to the whole body.

Minor changes in this amendment are summarized below:

- Change in Therapeutic Area Head (page 3, deleted [REDACTED] and added [REDACTED])
- Section 14.2, updated investigator responsibilities and confidentiality requirements
- Section 11.2.6, updated to ensure all serious adverse events (SAEs) will be followed until resolution or until the AE is no longer serious.
- Minor editorial and administrative changes (including changing *document to form*, and punctuation edits)

References:

## **1. JUSTIFICATION FOR AMENDMENT**

Significant changes included in this amendment are summarized below:

- The Medical Monitor / Emergency Contact Information has been changed for Japan.
- The following sections were updated to meet local regulatory requirements: Title Page, Protocol Summary, 7.2, 11.6, 14, 14.6, 14.8, 15.1, 15.3, and 16.2.

In addition, minor editorial changes have been made.

1. LIST OF ABBREVIATIONS

Table 1: Abbreviations and Specialist Terms

| | |
|---------------------|--|
| AE | Adverse event |
| ALT (SGPT) | Alanine transaminase (serum glutamate pyruvic transaminase) |
| ANCOVA | Analysis of covariance |
| APR | Apremilast |
| AST (SGOT) | Aspartate transaminase (serum glutamic oxaloacetic transaminase) |
| ATC | Anatomical Therapeutic Chemical |
| AUC | Area under the curve |
| AUC ₀₋₁₂ | Area under the plasma concentration-time curve from time zero to 12 hours postdose |
| AUC _{0-t} | Area under the plasma concentration-time curve from time zero to the last quantifiable concentration |
| AUC ₈₅ | Area under the curve for the number of ulcers from baseline to Week 12/Day 85 |
| BD | Behçet's disease |
| BDCAF | Behçet's disease Current Activity Form |
| BID | Twice daily |
| BMI | Body mass index |
| BSAS | Behçet's Syndrome Activity Score |
| CI | Confidence interval |
| C _{max} | Maximum observed plasma concentration |
| CMH | Cochran-Mantel-Haenszel (test or weights) |
| CRF | Case report form |
| DMC | Data Monitoring Committee |
| EAIR | Exposure-adjusted incidence rate |
| ECG | Electrocardiogram |
| ET | Early termination |
| GI | Gastrointestinal |
| IL | Interleukin |
| IP | Investigational product |

| | |
|------------|---|
| IRT | Interactive Response Technology |
| ITT | Intent-to-Treat |
| LOCF | Last observation carried forward |
| MCS | Mental Component Summary |
| MedDRA | Medical Dictionary for Regulatory Activities |
| MMRM | Mixed-effects model for repeated measures |
| PCS | Physical Component Summary |
| | |
| | |
| | |
| PGA | Physician's Global Assessment |
| | |
| PP | Per Protocol |
| PRO | Patient Reported Outcome |
| PT | Preferred term |
| QOL | Quality-of-life |
| SAE | Serious adverse event |
| SAP | Statistical analysis plan |
| SD | Standard deviation |
| SE | Standard error |
| | |
| SI | Standard international (unit) |
| SOC | System organ class |
| TEAE | Treatment-emergent adverse event |
| t_{\max} | Time to maximum observed plasma concentration |
| ULN | Upper limit of normal |
| VAS | Visual analog scale |
| WHODD | World Health Organization Drug Dictionary |

2. INTRODUCTION

This statistical analysis plan (SAP) describes the analyses and data presentations for Celgene's protocol CC-10004-BCT-002 "A Phase 3, Multicenter, Randomized, Double-blind, Placebo-controlled Parallel Group Study, followed by an Active-Treatment Phase to Evaluate the Efficacy and Safety of Apremilast (CC-10004) in the Treatment of Subjects with Active Behçet's Disease," Amendment 1 and Amendment 1.1 DE, which were issued on 02 FEB 2016 and 05 JUL 2017 (for German sites only), respectively. It contains definitions of analysis populations, derived variables and statistical methods for the analysis of efficacy and safety.

Throughout this SAP, the treatment arms will be referred to as the 30 mg twice daily (BID) group and the placebo group. The purpose of the SAP is to ensure the credibility of the study findings by pre-specifying the statistical approaches for the analyses of study data prior to database lock and the data analyses. This SAP will be finalized and signed prior to the clinical database lock for the first analysis (at 12 weeks).

These analyses include:

- Week 12 data analyses: clinical efficacy and safety analyses based on a database cut at Week 12/Visit 9 after all subjects have completed Week 12/Visit 9 or have discontinued early at or prior to Week 12, including Early Termination and Observational Follow-up visits (referred as the 12-week database). The treatment comparisons during Placebo-controlled Treatment Phase and the safety analysis for the Placebo-controlled period will be based on this database lock;
- Analyses of efficacy up to Week 28 and safety with at least 100 subjects with at least 1 year of apremilast exposure (referred as the second database);
- Week 68 analyses: clinical efficacy and safety analyses when all subjects have completed the Active Treatment Phase and/or 4-week Posttreatment Observational Follow-up Phase or have discontinued early;

In addition, for German sites only:

- Analyses for the optional Open-label Extension Phase for subjects from German sites who choose to enter the optional Open-label Extension Phase after completing the Active Treatment Phase.

All statistical analyses detailed in this SAP will be conducted using *SAS*® 9.2 or higher.

3. STUDY OBJECTIVES

3.1. Primary Objective

The primary objective is to evaluate the efficacy of apremilast in the treatment of oral ulcers in active Behçet's disease.

3.2. Secondary Objectives

The secondary objectives of the study are:

- To evaluate the efficacy of apremilast in subjects with active Behçet's disease
- To evaluate the effect of apremilast on Patient Reported Outcomes (PROs) in subjects with active Behçet's disease

3.3. Safety Objective

- To evaluate the safety and tolerability of apremilast in subjects with active Behçet's disease

4. INVESTIGATIONAL PLAN

4.1. Overall Study Design and Plan

This is a Phase 3, multicenter, randomized, double-blind, placebo-controlled, parallel group study, followed by an active-treatment extension phase to evaluate the efficacy and safety of apremilast (CC-10004) in the treatment of subjects with active Behçet's disease (BD).

Approximately 204 eligible subjects will be randomized 1:1 (102 subjects per group) to receive apremilast 30 mg BID (APR 30 BID), or identically-appearing placebo tablets BID for the 12-week Placebo-controlled Treatment Phase.

Upon completion of the Week 12 visit, subjects initially randomized to placebo will transition to APR 30 BID, while subjects initially randomized to APR 30 BID will continue on the same treatment during the 52-week Active Treatment Phase.

Subjects from German sites who complete Visit 14 of the 52-week Active Treatment Phase will have an opportunity to continue to receive APR 30 BID in an optional Open-label Extension Phase. Subjects who choose not to enter the optional Open-label Extension Phase will complete the 4-week Posttreatment Observational Follow-up Phase.

Subjects who discontinue at any time from the study for any reason are to enter the 4-week Posttreatment Observational Follow-up Phase.

The study will include the following:

- Screening Phase: up to 6 weeks
- Double-blind, Placebo-controlled Treatment Phase: 12 weeks
 - APR 30 BID
 - Placebo
- Active Treatment Phase: 52 weeks
 - APR 30 BID
- Optional Open-label Extension Phase for German Sites until apremilast is commercially available for BD or until the benefit/risk of apremilast is found not to be acceptable for BD, according to either the sponsor or health authority.
 - APR 30 BID
- Posttreatment Observational Follow-up Phase: – 4 weeks after the last dose (if a subject early terminates or, for subjects from German sites, choose not to enter the optional Open-label Extension Phase). Subjects from German sites who complete the optional Open-label Extension Phase do not need to complete the Observational Follow-up Visit.

Screening Phase

Screening procedures must be performed no more than 6 weeks prior to the start of study investigational product (IP) at Visit 2 (Day 1).

Treatment Phase

Subjects who qualify for enrollment will be randomized 1:1 to receive APR 30 BID or identically-appearing placebo tablets BID for the 12-week Placebo-controlled Treatment Phase. To mitigate potential gastrointestinal (GI) side effects dose titration will be implemented in the first week of this study. For dose titration, 10 mg, 20 mg and 30 mg apremilast tablets, or identically appearing placebo tablets, will be dispensed in dose titration cards at Week 0.

Active Treatment Phase

All subjects who complete the Placebo-controlled Treatment Phase will be eligible to enter the Active Treatment Phase. Subjects initially randomized to placebo will transition to APR 30 BID, while subjects initially randomized to APR 30 BID will continue on the same treatment during the 52-week Active Treatment Phase. To maintain the blind regarding the initial treatment assignment, all subjects will receive dose titration cards at Visit 9 (Week 12). Although only subjects initially randomized to placebo will be dose titrated during their first week of the Active Treatment Phase, all subjects entering the Active Treatment Phase will receive identically-appearing titration/treatment cards.

Posttreatment Observational Follow-up Phase

Subjects who discontinue at any time from the study for any reason are to enter the 4-week Posttreatment Observational Follow-up Phase to monitor changes in disease activity or safety parameters.

Optional Open-label Extension Phase

Subjects from German sites who complete Visit 14 of the 52-week Active Treatment Phase will have an opportunity to continue to receive APR 30 BID in an optional Open-label Extension Phase.

End of Trial

The End of Trial is defined as either the date of the last visit of the last subject to complete the study, or the date of receipt of the last data point from the last subject that is required for primary, secondary analysis, as pre-specified in the protocol and/or the SAP, whichever is the later date.

4.2. Study Endpoints

Study endpoints are described below, and the timing of when each assessment is to be collected is described in the protocol.

4.2.1. Efficacy Endpoints

4.2.1.1. Primary Efficacy Endpoint

The primary endpoint is area under the curve (AUC) for the number of oral ulcers from baseline through Week 12.

4.2.1.2. Secondary Efficacy Endpoints

- Complete response rate for oral ulcers at Week 12

[figure not shown]
- A complete response is defined as the proportion of subjects who are oral ulcer-free.
- Change from baseline in the pain of oral ulcers as measured by visual analog scale (VAS) at Week 12
- Complete response rate for genital ulcers at Week 12 for subjects who had genital ulcers at baseline
 - A complete response is defined as the proportion of subjects who are genital ulcer-free.
- Change from baseline in the pain of genital ulcers, as measured by VAS at Week 12 in subjects who had genital ulcers at baseline
- Change from baseline in disease activity as measured by Behçet's Disease Current Activity scores (BD Current Activity Form [BDCAF]) at Week 12
- Change from baseline in the BD Quality-of-Life (QoL) score at Week 12
- Change from baseline in Behçet's Syndrome Activity Score (BSAS) at Week 12
- Time to oral ulcer resolution (complete response), ie, the first instance when a subject has a complete response, during the Placebo-controlled Treatment Phase
- Proportion of subjects with no oral ulcers following complete response, ie, the first time when a subject has a complete response, during the Placebo-controlled Phase (Note: this will be the proportion of subjects with no oral ulcers following subject's first complete response during the Placebo-controlled Phase.)
- Number of oral ulcers following loss of complete response, ie, the first instance when a subject has a reappearance of oral ulcers following a complete response, during the Placebo-controlled Treatment Phase (Note: this will be the number of oral ulcers reported at the time of the first loss of complete response during the Placebo-controlled Phase.)
- Time to recurrence of oral ulcers following loss of complete response, ie, the first instance when a subject has a reappearance of oral ulcers following a complete response, during the Placebo-controlled Treatment Phase
- Change from baseline in the total score of the Static Physician's Global Assessment (PGA) of skin lesions (acne-like lesions, folliculitis and erythema nodosum) of BD at Week 12 in subjects who had BD skin lesions at baseline
- Proportion of subjects achieving an oral ulcer complete response (oral ulcer-free) by Week 6, after start of dosing, and who remain oral ulcer free for at least 6 additional weeks during the 12-week Placebo-controlled Treatment Phase

4.2.2. Safety Endpoints

Safety and tolerability as defined by the following:

- Type, frequency, severity, and relationship of the AEs to apremilast
- Number of subjects who prematurely discontinue IP due to any AE
- Frequency of clinically significant changes in vital signs, and/or laboratory findings

4.2.5. Derivations of Efficacy Endpoints

Efficacy assessments, as detailed in the following section, will be done at the intervals specified in the Table of Events, Table 1 in the protocol.

- The number of oral ulcers and genital ulcers will be counted at each study visit, at ET and Observational Follow-up visits following the Placebo-controlled or Active Treatment Phase. For females, both vulvar and vaginal ulcers will be considered for genital ulcers.
- The AUC from baseline to Week 12/Day 85 (AUC_{85}) is the sum of the AUCs in each time interval specified by the dates of the visits. The individual AUC for any given time interval is calculated based on the linear trapezoidal method, which uses linear interpolation between data points to calculate the AUC. The AUC_{85} can be calculated as follows:

$$AUC = p * \sum_{k=2}^8 \frac{1}{2} (C_k + C_{k+1})(t_{k+1} - t_k), \quad k = 2, 3, \dots, 8,$$

and

$$p = \frac{(85-1)}{(t_9-t_2)} = \frac{84}{(t_9-t_2)} p = \frac{(85-1)}{(t_9-t_2)} = \frac{84}{(t_9-t_2)}.$$

where C_2, C_3, \dots, C_9 are the number of ulcers at each visit from Visit 2/Baseline to Visit 9/Week 12, and t_2, t_3, \dots, t_9 are the ulcer assessment dates for Visit 2/Baseline to Visit 9/Week 12. When Visit 9/Week 12 does not exactly coincide with Day 85, the AUC through Week 12 will be adjusted for the actual study duration by dividing the total AUC by total study duration (in days) and multiplying this quantity by 84 days.

- The multiple imputation method will be used to impute missing oral ulcer counts when deriving the primary efficacy endpoint of AUC for the number of oral ulcers.

- AUC using a last observation carried forward (LOCF) approach to impute missing assessments at Week 12 will be used as a sensitivity analysis. If a subject has no post baseline ulcer assessment excluding the value obtained at the Observational Follow-up Visit, the baseline value will be carried forward for calculation. If there is a missing oral ulcer assessment between two visits or time points with assessments within a period, the AUC will be calculated based on the preceding and subsequent ulcers count.
- The LOCF approach will also be used for all other efficacy endpoints based on oral or genital ulcers count including calculating the cumulative number of oral ulcers per subject at all scheduled visits from baseline to Week 12. Of note, the cumulative count does not distinguish new occurrence of ulcers or the same ulcers appeared previously.
- The number of subjects who are oral ulcer-free (complete response) at Week 12 will be determined. Similarly, the complete response for genital ulcers at Week 12 will be determined for subjects who had genital ulcers at baseline. Subjects with missing data at Week 12 will be classified as non-responders. A sensitivity analysis with LOCF approach will also be conducted.
-
- The time to oral ulcer resolution is defined as the time interval in weeks from the date of first dose of IP to the date of first complete response with oral ulcer-free during the Placebo-controlled Treatment Phase. For subjects without any post-baseline oral ulcer assessment, the time to oral ulcer resolution will be censored to Day 1 of the placebo-controlled period; for the rest of the subjects who have a post-baseline assessment but have not achieved the complete response during Placebo-controlled Treatment Phase, the time to event will be censored at the last oral ulcer assessment date during the Placebo-controlled Treatment Phase
- Time to oral ulcer recurrence is defined as the time interval in weeks from the date of first complete response to the first reappearance of oral ulcers during the Placebo-controlled Treatment Phase. This analysis will only be conducted for subjects who are complete responders prior to Week 12. For subjects without ulcers recurrence following a complete response during the Placebo-controlled Treatment Phase, the time to event will be censored to the last oral ulcer assessment date during the Placebo-controlled Treatment Phase; for subjects without any ulcer assessment following the first complete response, the time to event will be censored to the first complete response date.
- For continuous endpoints including pain of ulcers as measured by VAS, BDCAF scores, total scores of PGA, BD QoL scores, and BSAS scores, the LOCF imputation approach will be used for subjects whose Week 12 assessment is unavailable. Similar to number of ulcers, if a subject has no post baseline assessment of endpoints above

excluding the value obtained at the Observational Follow-up Visit, the baseline value will be carried forward for calculation.

- Additional derivations including 3 patient reported outcome (PRO) endpoints are provided below:
 - Two separate pain VAS scales (100 mm) for oral and for genital ulcers will be completed by the subject and recorded on a secure, validated hand-held device. Subjects will be asked to click on the VAS line at the point that represents the severity of their pain during the previous week, with zero (the left-hand end of the scale) representing no pain and 100 mm (the right-hand end of the scale) representing the worst possible. The change from baseline will be determined. A negative change from baseline indicates improvement.
 - Behçet's Disease Current Activity Form (BDCAF) was developed for the International Scientific Committee on Behçet's Disease for routine monitoring of subjects, as well as for clinical studies ([Lawton, 2004](#)). The questionnaire is administered to the subjects by the investigator (Investigator will complete the form on a secure, validated hand-held device), and disease manifestations over the previous 4 weeks are quantified on a 12-point scale, with a higher score indicating higher level of activity, which is the sum score of 12 questions. A negative change from baseline indicates improvement.
 - Physician's global assessment (PGA) of BD related skin lesions (on skin lesions except oral/genital ulcers) will be completed by the investigators.
 - 
 - The Behçet's Disease Quality of Life (BD QoL) questionnaire was developed to measure the influence of BD on a subject's life ([Gilworth, 2004](#)). It consists of 30 self-completed items that measure disease-related restrictions on the subject's activities and the subject's emotional response to these restrictions. The BD QoL measure will be completed by the subject on a secure, validated hand-held device. The total score will be the summary of all 30 items (each yes scores 1 and each no scores 0). For possible missed items collected on the paper, the total score will be calculated using the following formula: [(sum of score of nonmissing items)/(total number of nonmissing items)]*total number of items on questionnaire. The total score ranges from 0-30, with zero representing no influence of BD on a subject's quality of life, and 30 representing the most severe influence. A negative change from baseline indicates improvement.
 - The Behçet's Syndrome Activity Score (BSAS) ([Forbess, 2008](#)) contains 10 questions, including assessments of the number of new oral and genital ulcers and skin lesions; assessment of the GI, CNS, vascular, and ocular involvement; and the assessment of the subject's current level of discomfort. The item scores are

totaled to create a score ranging from 0 to 100, with a higher score indicating higher level of activity; a negative change from baseline indicates improvement. The BSAS will be completed by the subject on a secure, validated hand-held device. If any BSAS question has the missing answer, the total score will be calculated based on the same formula used for BD QoL.

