10. EFFICACY ANALYSIS

10.1. General Approaches to Efficacy Analyses

The efficacy analyses will be based on the ITT population, and analyses of the primary efficacy endpoint will also be provided using the PP population. Statistical comparisons will be made between the apremilast group and the placebo group using 2-sided tests and the overall significance level will be maintained at 0.05.

All efficacy endpoints will be summarized by time points per the report conventions in Section 5.1. Analyses of the primary endpoint, secondary [REDACTED] endpoints assessed during the Placebo-controlled Period will be presented by randomized treatment group, Placebo and 30 mg BID. During the Active Treatment Phase, data will be presented by treatment sequence, i.e., Placebo/30 mg BID, or 30 mg BID/30 mg BID.

Efficacy results that will be considered statistically significant are described in Section 10.2.1. All statistical tests will be conducted at the $\alpha = 0.05$ (2-sided) level, and 2-sided p-values will be reported.

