10.2.3. Analyses of Secondary Efficacy Endpoints

Frequency counts and percentages will be provided for categorical variables including oral ulcer complete responders at Week 12, and genital ulcer complete responders at Week 12 for subjects who had genital ulcers at baseline. The proportions of complete responders in the two study treatment groups will be compared using a 2-sided Cochran-Mantel-Haenszel (CMH) test with significance level of 0.05, controlling for stratification factors including sex (male, female) and region (Japan, Other). Subjects who have discontinued early prior to Week 12 or who do not have data at Week 12 will be regarded as non-responders at Week 12. A sensitivity analysis using LOCF approach will be performed. The complete response rate based on the approach of NRI, or LOCF or the observed data will be provided for each time point during Placebo-controlled Treatment Phase.

Similarly, the proportion of subjects with no oral ulcers or no genital ulcers following subject's first complete response during Placebo-controlled Treatment Phase will be analyzed. The subjects who have a complete response prior to Week 12 but have no oral ulcers or genital ulcers assessment following subject's first complete response through Week 12 assessment will be excluded when summarizing each endpoint. The treatment comparison will only be conducted if appropriate.

The proportion of subjects achieving an oral ulcer complete response (oral ulcer-free) by Week 6, after the start of dosing, and who remain oral ulcer free for at least 6 additional weeks during the 12-week Placebo-controlled Treatment Phase will be analyzed similarly as the complete response rate as described above. Only those subjects who are oral ulcer-free by Week 6 and remain oral ulcer free for at least 6 consecutive weeks during the 12-week Placebo-controlled Treatment Phase will be considered as a responder; otherwise, subjects will be considered as non-responders. In case an oral ulcer assessment is missing at a visit, the LOCF approach will be used to impute missing assessments up to the ET visit or the last scheduled visit on or prior to date of treatment discontinuation, whichever is later.

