The number of oral ulcers following subject's first loss of a complete response will be summarized for subjects who have a complete response prior to Week 12. The number of oral ulcers will be summarized as zero for subjects who had no reappearance of oral ulcers following a complete response prior to Week 12. The comparison between two treatment groups will be performed using ANCOVA model with the treatment, sex and region as factors and baseline number of oral ulcers as a covariate. Within-group LS means, the associated SEs, and treatment differences in LS means, the associated SE, and associated 2-sided 95% CIs and 2-sided p-values will be derived from the model. The treatment comparison will only be conducted if appropriate.

The summary tables with descriptive statistics for number of oral ulcers and general ulcers will be presented by treatment group at all applicable analysis visits.

Summary tables for change from baseline with descriptive statistics will be presented for continuous variables including pain VAS of oral ulcers, pain VAS of genital ulcers, BD Current Activity Form Scores, BD QoL scores, BSAS scores,

, and total score of the Static PGA of skin lesions by treatment group at all applicable visits per study period. For the PGA, only subjects who had BD skin lesions at baseline will be included. For the pain VAS of genital ulcers, only subjects who had genital ulcers at baseline will be included.

The LOCF approach will be used to impute the missing assessment at Week 12 for the following endpoints: pain VAS of oral ulcers, pain VAS of genital ulcers, BD Current Activity Form Scores, BD QoL, and BSAS. The change from baseline at Week 12 (LOCF approach) will be compared between the placebo and the APR 30 BID group using ANCOVA model with change from baseline at Week 12 as the response variable, treatment, sex and region as factors and baseline value as a covariate. Within-group LS means, the associated SEs, and treatment differences in LS means, the associated SE, and associated 2-sided 95% CIs and 2-sided p-values will be derived from the model. A sensitivity analysis for change from baseline in the pain VAS of oral ulcers at Week 12 will be conducted using mixed-effects model for repeated measures (MMRM) with treatment, visit, treatment-by-visit interaction, sex and region as factors and baseline value as a covariate. An unstructured covariance matrix that is homogeneous across treatment groups is to be used.

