The frequency distributions for categorical changes from baseline for VAS (-100 to 100 inclusive in 25 increment for each interval) , BD QoL (< -20 to ≥ 10 in 5 increment for each interval), BD BSAS (< -60 to ≥ 40 in 20 increment for each interval)

will be summarized by time point A shift table from baseline to applicable analysis visits will be provided for number of oral ulcers, genital ulcers, the Behçet's disease activity index (0 to 3, 4 to 8 and 9 to 12), and PGA of skin lesions scales components (None, Mild, Moderate, and Severe).

Analyses of time to oral ulcer resolution and time to recurrence of oral ulcers following the first complete response during the Placebo-controlled Treatment Phase will use Kaplan-Meier method to estimate the median resolution/ recurrence time and its 2-sided 95% CIs. The stratified log-rank test will be used for calculating 2-sided p-values for treatment comparison. The hazard ratio and 2-sided 95% CIs will be estimated using a stratified Cox model. For the time to oral ulcer resolution, the baseline number of oral ulcers will be included as covariate in the Cox model. The treatment comparison will only be conducted if appropriate.

Kaplan-Meier curves for time to event endpoints will be provided by treatment group.

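### Ranks 11 and 12 of the testing sequence, and rank 10 by implication, compare only subjects who cleared, yet they gate two randomised comparisons under an undefined condition (minor)

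*SAP*

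**What the plan says.** SAP 10.2.1 tests the 14 endpoints of Table 4 in order at two-sided 0.05 and stops at the first failure. Protocol 10.6.1.1 leaves the order to the SAP.

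- **Rank 10** (no oral ulcers after first complete response). No denominator is stated. SAP 10.2.3 drops one group, "The subjects who have a complete response prior to Week 12 but have no oral ulcers or genital ulcers assessment following" that response, which implies a responder denominator. SAP 10.1 says "The efficacy analyses will be based on the ITT population", which leaves an ITT reading open.
- **Rank 11** (time to recurrence). SAP 4.2.5: "This analysis will only be conducted for subjects who are complete responders prior to Week 12".
- **Rank 12** (ulcer count at loss of response). SAP 10.2.3: it "will be summarized for subjects who have a complete response prior to Week 12", with zero entered if there is no recurrence. The test is an "ANCOVA model with the treatment, sex and region as factors and baseline number of oral ulcers as a covariate".
- **Ranks 13 and 14** (change in skin PGA; change in genital ulcer pain). Both are restricted only by status at baseline.

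For ranks 10 and 12, and again at the end of the paragraph on the two time-to-event endpoints (ranks 6 and 11), SAP 10.2.3 adds: "The treatment comparison will only be conducted if appropriate". No criterion is given. SAP 10.2.1 provides nominal p-values for tests blocked by an earlier failure, but does not say what happens to the sequence when a test is judged inappropriate.

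**The concern.** Clearing before Week 12 is a post-randomisation outcome that the drug is expected to change. Subjects who clear on placebo may be a milder group than those who clear on apremilast, so randomisation does not protect a comparison between them. Subjects who clear earlier also have longer in which to recur. Ranks 10 and 12 make no allowance for this, and the rank 12 model has no term for time at risk. Ranks 10–12 are reached only after ranks 5–7, all clearance endpoints, have succeeded, which is when the responder sets are most likely to differ.

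Two things are at stake. A formal claim at ranks 10–12 could be read as randomised evidence on recurrence. A failure there, possibly for reasons unrelated to recurrence, blocks formal testing of ranks 13–14. The open condition also lets the confirmatory sequence depend on a choice made after data are seen.

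**Working it through.** **The plan's own figures.** The plan gives no power or recurrence figure for ranks 10–14. Its one calculation, for the primary endpoint, reproduces: 2 × (1.960 + 1.282)² × 144² / 66² ≈ 100.1, so 101 per group by the normal approximation. By the exact t-test the smallest size is 102 per group, with power 90.3%. The 102 per arm is used below.

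**Who is in the set.** Protocol 1.3 gives Phase 2 clearance at Day 85 as 70.9% versus 28.6%. Applied to this trial: 102 × 0.709 = 72 and 102 × 0.286 = 29. The set in the SAP is clearance at any visit before Week 12, for which no rate is given. These counts show only the likely imbalance.

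**The ranks side by side.**

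| Rank | Set | Unequal follow-up handled? | Appropriateness condition? |
|---|---|---|---|
| 10 | responders (implied) | no | yes |
| 11 | responders (explicit) | yes, by censoring | yes |
| 12 | responders (explicit) | no | yes |
| 13, 14 | baseline-defined | not applicable | no |

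**Follow-up alone.** Assume the same recurrence risk of 0.15 per visit in both arms, with 4.3 later visits on apremilast and 3.4 on placebo (values from the first simulation below). The chance of staying clear is then roughly 0.85^4.3 = 0.50 versus 0.85^3.4 = 0.58. Rank 10 would lean to placebo with no difference in recurrence.

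**First simulation (illustration).** Each subject moves weekly between clear and ulcerated, seen at Weeks 1, 2, 4, 6, 8, 10 and 12. There are 102 per arm, and clearing is calibrated to 70.9% and 28.6% at Week 12. Weekly recurrence is 10–30% and equal in both arms, as is the count at recurrence. A severity term that slows clearing and raises recurrence is either absent or has SD 0.8 on the log-odds scale. No dropout. Responder sets were 94–102 on apremilast and 36–68 on placebo. The nominal rate is 2.5% each way.

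- Rank 10, responders only: favoured placebo in about 4–27%.
- Rank 12: favoured placebo in about 3–17%.
- Rank 10 on ITT with never-clear as failure: favoured apremilast in 13–97%.

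**Second simulation, different assumptions.** Recurrence hazard was 0.08 per week in both arms, with severity effects from none to strong and about 58 placebo and 85–97 apremilast responders. Rank 11 favoured placebo in 2–15% and apremilast in 0.3–3.6%. Rank 12 favoured placebo in 11–32% and apremilast in at most 0.4%. When treatment did not affect clearing, every rate was about 2–3%. The departure therefore arises when treatment changes who clears and when.

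**Why the rank 10 denominator matters.** Assume 80% versus 50% ever clear and 60% of clearers stay clear in both arms. On ITT this is 0.80 × 0.60 = 48% versus 0.50 × 0.60 = 30%, with power 0.75. Among responders it is 60% versus 60%, a rejection rate of 0.05.

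**Size of rank 14.** Phase 2 had 10 + 6 = 16 of 111 subjects with baseline genital ulcers: 204 × 16/111 ≈ 29. The size of the skin-lesion subset (rank 13) is not given.

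**The case against.** The strongest reply is that the restriction comes from the protocol's own endpoints: recurrence is undefined for a subject who never clears, and SAP 4.2.5 discloses the restriction. That stands for description. It does not make the comparison a randomised one.

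The order of low-ranked endpoints is also the sponsor's choice, and no net gain in power from reordering is shown. That stands. With 15 versus 14 subjects, a genital pain t-test has power of about 25%, 55% and 74% at assumed standardised effects of 0.5, 0.8 and 1.0, so it would often stop the sequence itself.

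Stopping at a test not done is the natural reading of SAP 10.2.1. That is fair, but it is unstated. Reaching rank 6 through the appropriateness sentence rests on where the sentence sits in its paragraph. The direction and PGA points are drafting gaps: two-sided wording is conventional, and Protocol 10.6.1.3 supplies ANCOVA for continuous endpoints.

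A reader might infer more than the documents support:

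- *That familywise error is broken.* Under stop-at-first-failure it is controlled for the hypotheses actually tested. The trouble is what ranks 10–12 mean, and the open condition.
- *That responder selection strongly inflates rank 11 in favour of apremilast.* Simulations can give up to 65%, but without a severity term this comes from recurrences that heal unseen between visits. With the same responder set seen weekly, the rates were 2.4–3.5% for apremilast and 1.9–2.9% for placebo, about nominal.
- *That a given share of trials would be blocked before rank 13.* This needs recurrence rates and ulcer counts at first recurrence, and the documents give neither. The Phase 2 Day 85 means cannot stand in, because they include subjects who never cleared.
- *That an ITT denominator turns rank 10 into a randomised test of recurrence.* It is randomised, but as shown above it mostly re-tests clearing.

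**Conclusion.** The concern holds as a minor one. From the text, ranks 11 and 12 are responder-set comparisons; rank 10 is one only by implication. None is a randomised comparison of recurrence, none need hold its nominal level, and together they gate two comparisons that are randomised within baseline subsets. The condition for making the comparison is undefined.

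Confidence is high on the structure and low on the size. The percentages rest on assumed recurrence rates and an assumed link between severity, clearing and recurrence. They illustrate that the level can be missed and are not bounds; the direction could differ under other assumptions.

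The harm is contained. The primary endpoint and ranks 2–9 do not use the responder set, although the open condition as worded also touches rank 6. Ranks 13–14 keep nominal p-values if blocked. Rank 5 already gives a formal durability test on all ITT subjects.

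**What to change.** Before unblinding, in the SAP:

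1. **Table 4.** Place the three post-response endpoints after skin PGA and genital ulcer pain, or make them descriptive. Label them as non-randomised comparisons in the responder set. If they become descriptive, record that in SAP Section 14, because Protocol 10.6.1.1 says the listed endpoints will be tested.
2. **SAP 10.2.3.** Delete the appropriateness condition for every endpoint kept in Table 4, including rank 6, and state that the sequence stops at a test that cannot be computed.
3. **Rank 10.** State the denominator. If all ITT subjects are used with never-clear as failure, describe the result as a composite of clearing and staying clear, not as evidence on recurrence; the non-randomised label then does not apply to it.
4. **Housekeeping.** SAP 4.2.5 gives an LOCF rule "For continuous endpoints including pain of ulcers as measured by VAS, BDCAF scores, total scores of PGA, BD QoL scores, and BSAS scores", but the ANCOVA comparison in SAP 10.2.3 is listed "for the following endpoints: pain VAS of oral ulcers, pain VAS of genital ulcers, BD Current Activity Form Scores, BD QoL, and BSAS". Add PGA total score to that list. State that a gate opens only for a result favouring APR 30 BID.

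The cost is wording. Reordering uses no alpha and needs no protocol amendment. The real downside is that any post-response endpoint still formally tested ranks lower, behind a genital pain test of about 29 subjects if the Phase 2 share holds.
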